6.1.2 Training Phase

The first step in evaluating the ability of the GeneXpert cartridge to distinguish benign from malignant disease, is to establish a decision rule specific for FNA material in the cartridge. Only gold standard pathology on core biopsy samples is used as a standard for comparison during the training phase; results from FNA cytology will not be considered when determining the decision rule. Clinical considerations lead us to target a sensitivity of at least 0.90. Accordingly, we will fix sensitivity at 0.90, selecting the threshold on cumulative methylation to achieve that level, and reporting the conditional specificity along with confidence intervals.

6.1.3 Test Phase

Both primary objectives require the comparison of cartridge results to binary diagnoses made by the study pathologist, so statistical methods for the two objectives are identical. Cumulative methylation values will be calculated for each sample and disease status predicted according to the rule locked down in the training phase. Sensitivity and specificity will be reported, along with exact binomial confidence intervals.

6.1.4 Subgroup Analysis

This study will include women who were referred for mammography after presenting with symptomatic disease as well as asymptomatic women who were identified in the course of routine screening, and it is possible that the assay performs differently in these two populations. Accordingly, in addition to overall performance, we will evaluate and report performance in each of these populations separately.

6.2 Secondary Objectives

Spearman rank correlation will be used to compare the DNA methylation levels as measured on the cartridge to measurements obtained by QM-MSP. Individual genes will be evaluated, as well as the cumulative methylation index. Likewise, Spearman correlation will be used to compare levels of ER/PR/Her2 and Ki67 as measured by the study pathologist, with those obtained using the cartridge.

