1.3 Rationale and Preliminary Data

Assaying hypermethylated genes in fine needle aspirates of suspicious breast lesions that have been detected by ultrasound could help rapidly identify malignant tumors, where the methylation marker test is predicted to be positive. On the other hand, the test will score negative for the methylation markers if lesion is benign since the lesion would contain low or no detectable levels of methylation (9),(6;7). In the last two years, using QM-MSP, we analyzed training and test sets of primary tumors from USA, China and Africa and developed an optimal methylated gene marker panel whose performance is at, or exceeding 90% sensitivity and specificity.

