1.4 Objectives

1.4.1 Primary objectives:

- 1) To determine if DNA methylation profile of 10 genes in the automated GeneXpert Cancer Detection cartridge correlates with diagnosis based on the gold standard of histopathology of the core biopsy or resected sample.
- 2) To determine if DNA methylation profile of 10 genes as determined in the automated GeneXpert Cancer Detection cartridge correlates with FNA cytology.

1.4.2 Secondary objectives:

- 1) To compare the results of gene methylation based prediction of the FNAs as malignant or benign by the GeneXpert Cancer Detection cartridge to our known laboratory assay, quantitative multiplex-methylation specific PCR (QM-MSP).
- 2) To compare QM-MSP results of FNA with QM-MSP results of section of the biopsy or resected tissue.
- 3) To determine if the expression of ER/PR/Her2 and Ki67 in FNAs of suspicious, methylation positive breast lesions correlates with expression of ER/PR/Her2 and Ki67 in FFPE sections of tumors.

2. Selection of Patients

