5.5 Additional analyses

In addition, FNA lysate or FFPE sections of the resected lesion or core biopsy will be accessed –

- a) To compare the predictions of the FNAs as malignant or benign and gene quantitation by the GeneXpert Cancer Detection cartridge to our known laboratory assay, quantitative multiplex-methylation specific PCR (QM-MSP).
- b) To perform the STRAT 4 assays in the cartridge using FFPE section of the core of the same malignant lesion to determine concordance between assays performed on FNAs versus resected or biopsied tissue

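### Secondary objective 1 asks whether cartridge and QM-MSP give FNAs the same malignant/benign call, but Section 6.2 plans only a Spearman correlation of methylation levels

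*Combined protocol and SAP*

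**What the plan says.** All references are to the combined protocol and SAP.

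- Secondary objective 1 (Section 1.4.2) is "To compare the results of gene methylation based prediction of the FNAs as malignant or benign by the GeneXpert Cancer Detection cartridge" with the laboratory's QM-MSP assay. The thing to be compared is a call.
- Section 5.5(a) names two tasks, again against QM-MSP: "To compare the predictions of the FNAs as malignant or benign and gene quantitation by the GeneXpert Cancer Detection cartridge".
- Section 6.2 supplies one method: "Spearman rank correlation will be used to compare the DNA methylation levels as measured on the cartridge to measurements obtained by QM-MSP". It is applied to each gene and to the cumulative index. No cross-tabulation, percent agreement or kappa for the two sets of calls appears anywhere.
- The training phase (6.1.2) "is to establish a decision rule specific for FNA material in the cartridge". No corresponding rule is stated for QM-MSP on FNA. The preliminary work in 1.3 says that, "using QM-MSP, we analyzed training and test sets of primary tumors from USA, China and Africa".
- On cytology, primary objective 1 asks whether the profile "correlates with diagnosis based on the gold standard of histopathology of the core biopsy or resected sample"; primary objective 2 uses FNA cytology as comparator without giving it that status. Section 6.1.3 says both need "comparison of cartridge results to binary diagnoses made by the study pathologist, so statistical methods for the two objectives are identical", and then: "Sensitivity and specificity will be reported, along with exact binomial confidence intervals".

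**The concern.** The objective is about calls and the planned statistic is about ranks. A Spearman coefficient could be reported, and look good, without anyone learning how often cartridge and QM-MSP would classify the same FNA differently. Two features make it a poor stand-in:

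- It uses no cut-off, so a badly placed one cannot show.
- Calculated over benign and malignant samples together, it is raised by the difference between the groups, even if the assays do not track each other within either group.

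The call comparison also lacks an input. With no QM-MSP rule for FNA fixed in advance, a cut-off chosen after the results are known could be tuned to improve agreement.

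A smaller point concerns wording. Sensitivity and specificity imply that the comparator is the truth. Only pathology is named the gold standard, so a specificity against cytology could be misread as cartridge accuracy.

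**Working it through.** **The plan's own figure.** Section 6.2.1 states that 80 per group at 90% gives a lower 95% bound of 80%. The exact interval for 72/80 is 81.2% to 95.6%. The statement holds and is not in dispute.

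**Model for calls versus ranks (assumed).** Both assays are normal with SD 1 in each group, and the malignant mean is 2 × 1.2816 SD above the benign mean. A cut-off at 1.2816 gives 90%/90%, the level used in 6.2.1. There are 80 malignant and 80 benign samples. The within-group correlation between assays is r. Rho is simulated; agreement comes from bivariate normal probabilities. The cartridge calls half the samples positive, so chance agreement is 0.5 and kappa = 2 × agreement − 1.

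*Effect of pooling, r = 0.* Agreement = 0.9 × 0.9 + 0.1 × 0.1 = 0.82; kappa = 2 × 0.82 − 1 = 0.64. Mean within-group rho is 0.00, yet pooled rho is 0.65.

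*Effect of the cut-off, r = 0.8.* Pooled rho is 0.925 and within-group rho 0.78 in every row, because moving a cut-off does not change ranks.

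| QM-MSP cut-off | QM-MSP sensitivity/specificity | Agreement | Kappa |
|---|---|---|---|
| well placed | 90%/90% | 91% | 0.825 |
| 0.5 SD off | 78%/96% or 96%/78% | 88% | 0.77 |
| 1 SD off | 61%/99% or 99%/61% | 80.5% | 0.61 |

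**Precision of the missing analysis (r = 0.8).** Positive and negative percent agreement are conditioned on the QM-MSP call, so the denominators are QM-MSP positives and negatives, not 80 per group.

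- Balanced case: 73/80, exact 95% interval 83% to 96%.
- Cut-off 1 SD too high: QM-MSP positives are 160 × (0.61 + 0.01)/2, about 50, leaving about 110 negatives. Model values of 0.991 and 0.722 give about 49/50 (89% to 99.9%) and 79/110 (62% to 80%). Overall, 0.805 × 160 is about 129/160 (74% to 86%). Counts are rounded separately and do not add exactly.

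**Cytology labels.** Assume a cartridge that is truly 90%/90% against histopathology, a 1:1 mix, cytology sensitivity Se of 85–95% and specificity Sp of 95–100%, and errors ranging from independent to fully shared. The apparent specificity is P(both negative), summed over the two groups, divided by (1 − Se) + Sp. The apparent sensitivity is the same with positives, divided by Se + (1 − Sp).

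- Lowest specificity (85%/95%, independent): (0.15 × 0.10 + 0.95 × 0.90)/1.10 = 0.870/1.10 = 79%.
- Highest specificity (95%/95%, shared): (0.05 + 0.90)/1.00 = 95%.
- Lowest sensitivity (85%/95%, independent): (0.85 × 0.90 + 0.05 × 0.10)/0.90 = 0.770/0.90 = 86%.
- Highest sensitivity (85%/100%, shared): 0.85/0.85 = 100%.

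**The case against.** The strongest reply on the main point is that the disagreement figures depend on an invented cut-off error. With both cut-offs well placed, rho and agreement rise together: r = 0, 0.5 and 0.8 give pooled rho 0.65, 0.82 and 0.925 and agreement 82%, 86.5% and 91%. Section 6.2.1 says the panel exceeds 90% sensitivity and specificity by QM-MSP, which presupposes some working rule, and 1.1.3 describes QM-MSP as feasible in core biopsy and rFNA material. All of that stands. A reader might infer that QM-MSP is misplaced on FNA, or that a high rho is likely to hide poor agreement. The documents support neither: they give no FNA cut-off and suggest no particular shift. What remains is that the planned statistic could not reveal such a problem and does not answer the stated objective.

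On cytology, the reply is that relabelling changes no number, and that cytology is already kept out of the decision rule in 6.1.2. That is right, so it is only a wording note. A reader might infer that the label always counts against the cartridge. It need not: shared errors can lift the apparent figures above the true 90%.

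A reader might also extend the point to secondary objective 2, Section 5.4 and Section 5.5(b). Those are matters of missing detail and are not part of this point.

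**Conclusion.** The point holds for the comparison of calls. Secondary objective 1 and 5.5(a) ask for it, 6.2 provides no method for it, and no QM-MSP rule for FNA is stated. Spearman is appropriate for the quantitation task and should stay.

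The illustrated size is a pooled rho of 0.65 from group separation alone, and agreement from 91% down to 80.5% at an unchanged rho of 0.925. These rest on the binormal 90%/90% model and assumed cut-off shifts, so they show what Spearman cannot detect, not what will be found.

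The cytology label is minor: under the stated assumptions, a true 90%/90% cartridge could show a specificity of about 79–95% and a sensitivity of about 86–100%, so the label can penalise or flatter it.

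A reader might take this as a flaw in the main accuracy result. It is not: the estimate against histopathology under primary objective 1 is unaffected. This should be corrected because it is cheap and a stated objective is otherwise unanswered.

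**What to change.** In Section 6.2:

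1. State the QM-MSP call rule for FNA and lock it before the test set is read.
2. Cross-classify cartridge and QM-MSP calls, each at its own locked threshold. Report positive, negative and overall percent agreement with exact 95% intervals; kappa is optional.
3. Keep Spearman for levels, reported within malignant and within benign as well as pooled.

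In Section 6.1.3, keep the table and exact intervals for primary objective 2, but label them positive and negative percent agreement with cytology.

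The cost is SAP wording, one stated call rule and a few tables from data already collected; no added patients or samples. The downside is that agreement may look less favourable than a pooled Spearman, with moderately wide intervals that depend on how QM-MSP divides the samples.

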1.3.3 Determination of receptor status

In addition to determining the methylation status of the tumor, sections or tissue lysate of the same lesion can be used in a separate cartridge on the GeneXpert® subtyping device to determine estrogen receptor (ER), progesterone receptor (PR), and HER2 status of the tissue which are key pathologic features responsible for determining treatment options. Thus, the assay can be successfully employed in underserved areas of the world in the future. This assay is completed in 1.5 hr. We tested FNAs of xenografts and successfully determined the status of the four markers in this cartridge for several breast cancer cell lines.

Summary: Identifying the optimal set of 10 methylated gene markers suitable for use in the US, China and Africa has been completed. Preliminary analysis of genes in the cartridge to determine their performance on FNAs was successful. With our help, CEPHEID has designed two cartridges to analyze a total of 10 genes by a quantitative multiplexed methylation specific PCR that uses actin as the internal housekeeping gene control. Preliminary analysis of FNA in the tumor subtyping has been partially successful. While the assay works with high level of accuracy using FFPE sections, conditions for optimal detection of the subtyping markers in FNA needs further work.

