5.4 STRAT4 subtyping assay

A cell lysate from a second unstained slide will be analyzed in the automated STRAT4 (ER/PR/HER2/Ki67) assay cartridge.

STRAT4 results will be compared to standard estrogen receptor (ER), progesterone receptor (PR), human epidermal growth factor receptor 2 (HER2) and Ki67 (ER/PR/HER2/Ki-67) by IHC/FISH performed routinely by the pathlab for comparative accuracy of the markers.

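### The only receptor analysis is a Spearman correlation of levels, which cannot deliver the accuracy (5.4) and concordance (5.5(b)) that the protocol asks of the receptor cartridge

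*Combined protocol and SAP*

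**What the plan says.** All references are to the combined protocol and SAP.

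- **Section 6.2 (Secondary Objectives)** holds the only statistical text on the receptor markers: "Spearman correlation will be used to compare levels of ER/PR/Her2 and Ki67 as measured by the study pathologist", compared with the cartridge values. It names no agreement measure, cut-off, interval or target.
- **Section 1.4.2, objective 3** asks whether expression "in FNAs of suspicious, methylation positive breast lesions correlates with expression of ER/PR/Her2 and Ki67 in FFPE sections of tumors".
- **Section 1.3.3** describes the cartridge as a means of determining ER, PR and "HER2 status of the tissue which are key pathologic features responsible for determining treatment options". It also reports that the assay is accurate on FFPE sections but that "conditions for optimal detection of the subtyping markers in FNA needs further work".
- **Section 5.4** compares the cartridge with receptor results "by IHC/FISH performed routinely by the pathlab for comparative accuracy of the markers".
- **Section 5.5(b)** runs the cartridge on FFPE core from the same malignant lesion "to determine concordance between assays performed on FNAs versus resected or biopsied tissue".
- **Section 6.1.3**, by contrast, treats the methylation call as a classification: "Sensitivity and specificity will be reported, along with exact binomial confidence intervals".

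**The concern.** Sections 1.3.3, 5.4 and 5.5(b) raise agreement questions: does the cartridge give the status that the routine laboratory gives, and does the FNA give the result that the tissue gives? Section 6.2 measures whether two sets of values rise together. A rank correlation is unchanged by any increasing transformation of either variable, so it carries no information on whether the cartridge's cut-off falls in the right place.

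This matters here because the protocol itself says that the assay performs well on FFPE but is not yet optimised on FNA. A loss of signal in FNA relative to a cut-off suited to FFPE is a plausible way for it to fail, and Spearman would not see it. The study could report a high rho and leave unknown how often ER, PR or HER2 status was called wrongly.

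Two smaller gaps go with this. The documents give no scale for HER2 and no rule for combining IHC with FISH, so the HER2 level to be ranked is undefined. The set of lesions to be analysed is also described differently in 1.4.2, 5.4 and 5.5(b).

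**Working it through.** **The plan's own figures.** The documents give no sample size, precision or target for the receptor endpoint, so there is nothing of its own to reproduce. The only precision figure (6.2.1: 80 per group, 90%, lower 95% bound 80%) concerns the methylation call. Clopper-Pearson for 72/80 gives 81.2% to 95.6%, which is consistent with it.

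**Inputs from the documents.** 165 malignant cases (2.1), 160 of them in the training and test phases; sensitivity of the methylation call fixed at 0.90 (6.1.2). The documents give no receptor prevalence, cartridge cut-off or size of shift, so the values below are assumptions shown over a range.

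**1. A high rho can coexist with wrong calls.** Let both scales be standard normal with identical ranks (rho = 1). The reference is positive above c = Φ⁻¹(1 − p), and the cartridge reads s SD too low against the same cut-off. Positive percent agreement is then PPA = [1 − Φ(c + s)]/p.

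| Prevalence p | c | Shift s | 1 − Φ(c + s) | PPA |
|---|---|---|---|---|
| 15% | 1.036 | 0.5 | 0.0622 | 0.0622/0.15 = 41% |
| 15% | 1.036 | 1.0 | 0.0209 | 0.0209/0.15 = 14% |
| 75% | −0.674 | 0.5 | 0.5693 | 0.5693/0.75 = 76% |
| 75% | −0.674 | 1.0 | 0.3724 | 0.3724/0.75 = 50% |

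With a bivariate-normal correlation of 0.9 (Spearman 0.89) and p = 15%, PPA is 72%, 38% and 14% at shifts of 0, 0.5 and 1 SD. Spearman is 0.89 in all three.

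**2. A perfect classifier can have a modest rho, if the reference is binary.** With an untied cartridge value and a reference in ordered groups with shares pᵢ, the largest possible Spearman is √(1 − Σpᵢ³). For two groups this is √(3p(1 − p)).

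- 10% positive: √(3 × 0.10 × 0.90) = 0.52
- 15%: 0.62
- 20% or 80%: 0.69
- 75%: 0.75
- 50%: 0.87
- Four ordered grades with assumed shares 40/30/15/15%: √(1 − 0.0978) = 0.95

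**3. Effect of restricting to methylation-positive lesions.** At sensitivity 0.90 the restriction leaves out 0.10 × 80 = 8 cancers per phase, or 16 of 160. Of all 165 cases, about 148 (0.90 × 165 = 148.5) remain.

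**4. Precision of percent agreement.** Exact intervals on about 148 cases, with true agreement near 90% (assumed):

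- HER2 positive 10%: 14/15, 68% to 100%
- HER2 positive 15%: 20/22, 71% to 99%
- HER2 positive 20%: 27/30, 73% to 98%
- HER2-negative agreement: lower bound about 83% to 84%
- ER or PR positive 70% to 80%: positive agreement 94/104 to 106/118, lower bound 83%; negative agreement 40/44 to 27/30, lower bound 78% to 73%

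**The case against.** The strongest defence is that 6.2 does what objective 3 asks. The objective is about correlation of expression, the planned statistic is a correlation of levels, and for an assay still being adapted to FNA a continuous-scale comparison is a reasonable secondary analysis. That stands. A reader might infer that Spearman fails objective 3 or should be dropped, and the documents support neither. The shortfall is against the aims in 1.3.3, 5.4 and 5.5(b).

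A reader might also infer that ties will make a good cartridge look poor. That needs a reference recorded as positive or negative. Section 5.4 says only that IHC/FISH is done routinely, and 6.2 speaks of levels. Graded reports are possible, and then the cap is near 1 (0.95 in the example). So the cap is conditional, whereas insensitivity to a cut-off shift holds on any scale. Likewise, the HER2 scale is undefined in the documents; it is not shown to be impossible to define.

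On the lesion set, a reader might see a contradiction. But 5.4 is silent on the set, 5.5(b) is a different comparison, and limiting objective 3 to lesions the first cartridge calls positive may be deliberate. Benign false positives would be expected to lack a routine receptor result or tumour section, so they would probably drop out. What remains is that the three sections do not state one set.

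Finally, no hypothesis test, success criterion or go/no-go decision depends on this endpoint. That limits the consequence but does not fill the gap.

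**Conclusion.** The concern holds as a mismatch between stated aims and planned statistic. Section 6.2 offers no measure of accuracy for 5.4 and no statistic of any kind for the FNA-versus-FFPE comparison in 5.5(b).

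The invariance of rank correlation to a shift is a mathematical fact and needs no assumption. Its size does: the range from 41% down to 14% positive agreement at 15% prevalence, with rho = 1, rests on an assumed normal scale, prevalence and shift, and no such shift has been shown for this cartridge. The cap of 0.52 to 0.87 applies only to a reference recorded as positive or negative.

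The endpoint is secondary, and the sensitivity and specificity of the methylation call are untouched. The change is still worth making before analysis: it uses data that the study collects anyway, and cut-offs chosen after the results are seen would bias the agreement upwards.

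**What to change.** In 6.2, and in 1.4.2 where the wording needs to match:

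- **Definitions.** Fix each marker's cartridge positivity cut-off before analysis; the documents state none, so the sponsor must supply it. Define the reference status for ER, PR and HER2, with HER2 taken from the combined routine IHC/FISH conclusion. Say whether the study pathologist (6.2) or the routine pathology laboratory (5.4) provides it.
- **Statistics.** Add overall, positive and negative percent agreement with exact intervals for ER, PR and HER2, once for FNA cartridge against IHC/FISH and once for FNA cartridge against FFPE cartridge. Report the number of invalid cartridge results. Keep Spearman as the supporting analysis of graded levels and for Ki67.
- **Analysis set.** State one set that reconciles 1.4.2, 5.4 and 5.5(b), for example all malignant lesions with valid paired results, with the methylation-positive lesions shown as a subset.

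**Cost.** Some wording and a few 2×2 tables, with no extra patients. If the sponsor had meant to run receptor cartridges only on methylation-positive lesions, about 16 more may be needed (10% of 160). The main drawback is imprecision: HER2-positive agreement will have a wide interval and will miss the 10-point precision that the plan sets for the methylation call. The protocol should say so in advance.

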6.2.1 Sample Size Considerations

Our sample size considerations are motivated by the need for precise estimates of performance, so that an apparently successful model can be carried forward with confidence. Our current methylated marker panel achieves both sensitivity and specificity higher than 90% for distinguishing between normal/benign and malignant disease when evaluated using QM-MSP, and so sample size requirements are calculated at that level. At the proposed sample size, at a sensitivity and specificity of 90%, the estimation errors for the conditional specificity are controlled at +/-10%.

In addition to 10 pilot patients, we will recruit 80 subjects in each group, in each of the two major phases (training and test). This number was selected to control the precision of the confidence intervals on sensitivity and specificity. Specifically, with a sample size of 80 in each group, and sens/spec of 90%, the performance can be estimated to within 10% percentage points (lower, 95% confidence bound =80%), a level of confidence we feel is appropriate for this study.

We estimate that 40%-50% of suspicious lesions will turn out to have malignant disease after path exam of the core biopsy, in which case the limiting factor in obtaining the necessary 330 lesions will be collecting 165 malignant cases. Assuming the lower value of 40% malignancy, we expect to have to enroll $165/0.4=413$ patients in order to obtain at least the required 165 cases. At the more extreme ends of the sampling distribution, there is a 10% chance that we can obtain the necessary cases in as few as 382 enrollments, and conversely a 10% chance of falling short even with 447 enrollments. Accordingly, after enrolling 382 subjects we will calculate rates of malignant and benign disease, and estimate total enrollment requirements, and continue enrollment as needed.

7. Adverse Event Reporting

Subjects will be contacted by phone 1-2 days post-FNA and core biopsy to assess adverse events. There is some complexity in this reporting as a core needle biopsy will immediately follow the FNA. The cause, FNA vs core biopsy, of the AE will be inseparable; therefore, determining which process led to the AE will be impossible.

Subjects will also be contacted by phone approximately 10-14 days post-FNA to assess adverse events. Bruising that is still present after 14 days will be considered an AE. If a subject reports bruising at 14 days, we will ask her to be seen by the breast imagers for assessment. A postFNA/biopsy hematoma that requires surgical evaluation will be considered a severe adverse event (SAE). All adverse events will be recorded and reported to the Clinical Research Office as well as to the IRBs as required by guidelines for adverse event reporting.

8. Records To Be Kept

In addition to the hospital chart, a separate patient study folder will be kept which will include the patient's signed, dated informed consent document.

9. Pathology Requirements

For laboratory/pathology samples:

Laboratory samples will be collected in the clinic by [name] or their qualified investigators at Johns Hopkins Imaging at Green Spring. Cytopathology will be assessed by [name] and a laboratory identifier will be provided. The [name] lab will measure methylation in all samples.

10. Data And Safety Monitoring Plan

This trial will be conducted in accordance with the Data and Safety Monitoring Plan (DSMP) of the Johns Hopkins University's Sidney Kimmel Comprehensive Cancer Center.

REFERENCES

4. Unger-Saldana K: **Challenges to the early diagnosis and treatment of breast cancer in developing countries.** *World J Clin Oncol* 2014, **5**(3):465-477.

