2.3 Subject Recruitment

Subjects will be recruited through the Johns Hopkins Imaging Center site at Green Spring. Women will be offered participation if they are recommended to have a breast core needle biopsy of a suspicious lesion.

3. Patient Registration

- Patients will undergo an informed consent process and subject registration number will be assigned.
- Registered patients will be tracked by patient log. This log will be submitted to the CRO on a periodic basis (quarterly, at minimum) until study closure and will include:
 - Subject name (or initials)
 - Registration number
 - Date of registration
 - Date of birth
 - Race

4. Study Calendar

	Baseline	Day of Procedure	Follow-Up 1 ⁽¹⁾	Follow-Up 2 ⁽²⁾
Informed Consent	X			
Eligibility Confirmed	X			
Patient registration	X			
PROCEDURES:				
- Fine Needle Aspiration (FNA)		X		
- Core needle biopsy of suspicious lesion		X		
OTHER ASSESSMENTS:				
Adverse Events call			X	X

¹: 1-2 days after procedure

²: 10-14 days after procedure

5. Study Parameters

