5.1 FNA Procedure: For Suspicious lesions

Women ages 18 or older who have been recommended for ultrasound guided core biopsy for a suspicious breast lesion at the Green Spring Johns Hopkins Imaging site will be recruited into the study.

The FNA will be performed on one ultrasound visible lesion per patient, using the method described by Fabian et. al. [21, 22] which is standard at Johns Hopkins and used by the breast imagers. When recommended for the core biopsy, participants are asked to abstain from aspirin and other medications/supplements related to blood clotting and platelet function outlined in the eligibility criteria for a week prior to the procedure. For the procedure, 1% lidocaine local anesthesia is delivered at the skin (1 to 5 cc) followed by deeper infiltration (about 5 to 10 cc) of 1% lidocaine with or without 1:100,000 epinephrine at the site of each lesion; this will also be used for the core needle biopsy, which will immediately follow the FNA procedure. When more than one eligible lesion is visible in the same patient, one random lesion will be selected.

NOTE: Buffered lidocaine may be used per investigator preference/institutional standard. Next, the FNA procedure itself is performed by sampling the lesion with a 22 to 25 gauge needle attached to a 5 ml syringe with 2-3 passes through each lesion using ultrasound guidance thus confirming accurate targeting. Additional lidocaine may be given if needed for discomfort. The core needle biopsy using standard of care procedures will then occur.

The standard post biopsy instructions, both verbal and written will be provided to all patients. An ice pack is applied to the breast(s) following the procedure, and the subjects are asked to wear a firm sports bra (alternatively, compression wraps or firm bandages may be used).

In our present study, where 1 FNA procedure consists of 2 to 3 passes of the needle into the suspicious lesion, the mean pain rating is 1-1.5 (on a scale of 10); this is consistent with publications from the University of Kansas and the Johns Hopkins study [21, 22]. We may also use a buffered 1% lidocaine so as to minimize the burning sensation associated with unbuffered lidocaine. With our present technique, we are experiencing an average epithelial cell yield of 10,000 cells, and about 10% of samples contain less than 5,000 cells. DNA methylation studies can be performed with as low as 300 cells.

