The above study plan will recruit 5 women with benign disease and 5 women with malignant disease to undergo FNA prior to core biopsy in the Pilot phase. 80 evaluable subjects with benign disease and 80 with malignant disease will be recruited for FNA prior to core biopsy in Training phase. An additional 80 women with benign disease and 80 women with malignant disease will be recruited for the Test phase if the criteria for the assay are met in the Training set. If not, the assay will be fine-tuned further in the lab with modifications to increase sensitivity and specificity.

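### Read literally, the last adverse event call (days 10-14) can come before the protocol's own 14-day bruising cut-offs, and no later contact is written for a woman still bruised on days 10-13

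*Combined protocol and SAP*

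**What the plan says.** The Study Calendar (section 4) has two contacts after the procedure, both AE phone calls. The first is on days 1-2. The second, in the last column, is timed by footnote 2 as "10-14 days after procedure". Section 7 gives the same timing a little more loosely: "approximately 10-14 days post-FNA to assess adverse events".

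Section 7 then sets two rules for bruising. The AE definition is "Bruising that is still present after 14 days will be considered an AE". The referral rule is "If a subject reports bruising at 14 days, we will ask her to be seen by the breast imagers for assessment".

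Four other provisions bear on the point:

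- Section 7 makes a hematoma needing surgical evaluation an SAE, with no day limit.
- Section 7 says of attribution: "The cause, FNA vs core biopsy, of the AE will be inseparable".
- Section 5.1 says: "The standard post biopsy instructions, both verbal and written will be provided to all patients". The content of those instructions is not shown.
- Section 10 places the trial under the institution's data and safety monitoring plan, which is not reproduced.

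**The concern.** The call schedule and the bruising rules do not fit together. A call made on day 11 is fully compliant, yet it takes place before a bruise can meet either cut-off. If the woman is still bruised, section 7 does not say what happens next, and the calendar has no later contact at which the question could be settled. A woman with the same bruise who is called on day 14 is asked to come in for assessment.

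Whether an event that the protocol itself defines is captured could therefore depend on which permitted day the staff happened to call. Bruising is the only event to which section 7 gives a day threshold and a referral step, and the two calls are the only safety assessments after the procedure in the calendar. At stake are the completeness of a minor safety record and the review of a woman whose bruise does not resolve.

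**Working it through.** No sample size, power or error-rate figure bears on this point, and the plan gives no figure of its own to reproduce. The check sets the call window against the two cut-offs.

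**Inputs.** Call window: days 10-14 (section 4, footnote 2; section 7). Referral trigger: bruising reported at day 14 (section 7). AE threshold: bruising present after day 14 (section 7). Later scheduled contacts: none (section 4).

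| Call day | Referral trigger reached? | Past day 14, so AE status can be judged? | Written next step if bruised |
|---|---|---|---|
| 10 | No | No | None |
| 11 | No | No | None |
| 12 | No | No | None |
| 13 | No | No | None |
| 14 | Yes | No, if taken strictly | Imager visit, which can settle AE status |

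**Count of days.** The window has 5 days. Days before the referral trigger: 4 of 5. Days not yet past day 14: 5 of 5. These are counts of permitted days. They are not probabilities, because the documents give no distribution of call days.

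**Who is affected.** Only women still bruised on a day 10-13 call. A woman with no bruise at the call is not affected, and a woman bruised on a day 14 call is referred.

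**Can missed AEs be counted?** An upper bound is N × b × f, where N is the number of women enrolled, b the share of them found bruised on a day 10-13 call, and f the share of those bruises that last past day 14. The documents give neither b nor f, so both are assumptions. To show the scale only, take b = 1% and let f run from 0 to 1:

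- Full study, expected enrollment to reach 165 malignant cases: 165/0.5 = 330 to 165/0.4 = 412.5, so 413 women. With f = 1: 330 × 0.01 = 3.3 to 413 × 0.01 = 4.1 women. With f = 0: none.
- Section 2.1's planning range of 382-447 gives 3.8 to 4.5 women with f = 1. By section 6.2.1 those limits are the 10% tails at 40% malignancy, so they are not on the same basis as the line above.
- Pilot and training only, since the further women "will be recruited for the Test phase if the criteria for the assay are met in the Training set": 5 + 80 = 85 malignant cases; 85/0.5 = 170 to 85/0.4 = 212.5, so 213 women. With f = 1: 1.7 to 2.1 women. With f = 0: none.

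If every call is made on day 14 or later, b = 0 and so is the bound. The true number also falls if women report lasting bruises unprompted or staff call back on their own initiative.

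**The case against.** The best counter-argument is that the referral rule need not mean calendar day 14. In section 7 it follows directly after the second call, which is the only scheduled occasion on which a woman could report a bruise at about that time, and the call window is itself approximate. Read this way, any bruise reported at the second call leads to an imager visit, and the visit can settle AE status. This is a plausible reading and would close the referral gap. It does not remove the point, because the text does not state it, footnote 2 gives the window without the qualifier, and the AE definition still looks to a time after day 14. The approximate wording allows a later call but does not require one.

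Three limits also stand. The text is silent on a bruise at days 10-13; it does not forbid action, and the call exists to assess AEs, so staff would hear of the bruise. The post-biopsy instructions and the monitoring plan are cited but not shown, and consent pages are not in the copy reviewed, so a prompt to self-report may exist there. A hematoma needing surgical evaluation is caught whatever the day, and since FNA and core-biopsy causes cannot be separated, a bruise record says little about the FNA alone.

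A reader might go further and infer that AEs will be missed, or that 80% of persistent bruises will be. The documents do not support this. Four of five is a count of days, and no call-day, bruising or persistence rate is given. Nor does anything here touch the accuracy results, which come from the cartridge and pathology and not from the phone calls.

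**Conclusion.** The point holds in a limited form. On a literal reading, a compliant second call can come before both bruising cut-offs, and the protocol text shown requires no later contact for a woman still bruised on days 10-13. A persistent bruise can then escape recording and assessment because of the day of the call. If the referral rule is meant to apply to the second call itself, these women are covered, but the sponsor would have to say so.

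Severity is low. The number of missed AEs cannot be derived; the per-1% figures rest wholly on assumed rates and start at zero. The conclusion assumes only that the unseen supporting documents do not already require a contact on or after day 14. Estimates of sensitivity and specificity are unaffected. It is still worth correcting, because two stated rules do not fit together and following them exactly can lose the event that the protocol defines.

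**What to change.** Amend footnote 2 of the Study Calendar and section 7 together:

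1. Keep the day 10-14 call and require a repeat call on or after day 14 for any woman still bruised on days 10-13. Alternatively, move the second call to days 14-16.
2. Use a single threshold, bruising present at 14 days or later, for both AE status and imager referral.

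The cost is wording in two places, plus one short extra call for the women still bruised on days 10-13 or a slightly later second call for everyone. The repeat call has the advantage of leaving the earlier contact in place for all other events.
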